**Application for Review of Human Research: IRB Protocol Summary
Biomedical Research**

Version 15: 8/17/2020

IRB# 824504

Names of Investigators:

Name	Department (all at UPenn)
[name]., Principal Investigator [name] [contact] [contact]	Psychiatry
[name]., Co-I	Psychiatry
[name]., Co-I	Psychiatry
[name], Study Physician	Medicine

PROTOCOL TITLE

1. Full Title

Effects of metformin on mood and cognition during nicotine withdrawal

2. Brief Title

Effects of metformin during nicotine withdrawal

STUDY SPONSORSHIP

1. Funding Sponsor

PA Department of Health

2. Primary Sponsor

University of Pennsylvania

ClinicalTrials.gov IDENTIFIER

NCT03593538

PROTOCOL ABSTRACT

There is a need for novel approaches to optimize smoking cessation treatment to help more smokers quit. Mood disturbance and cognitive deficits during nicotine withdrawal may be important treatment targets given their association with smoking relapse. In addition, factors such as HIV-1 infection may exacerbate abstinence effects on mood and cognitive deficits thus increasing the probability of smoking relapse among HIV-infected smokers (HIV+), compared to HIV-uninfected smokers (HIV-). We hypothesize that the FDA-approved medication, metformin, will attenuate withdrawal-related mood disturbance and cognitive deficits and we will explore whether HIV status moderates these effects. Using a well-validated abstinence challenge paradigm, we propose a placebo-controlled double-blind parallel arm study with one between-subjects factor of medication (low dose: 500 mg, high dose: 1500 mg, and placebo). Non-treatment seeking smokers (HIV-: n=54; and HIV+: n=30) will complete this 23-day study. After completing a baseline visit, subjects will complete 4 additional sessions (days 7, 14, 21, 23) to assess side effects, smoking rate, mood, craving, and withdrawal. Cognitive function will also be assessed on days 21 and 23. Subjects will be instructed to refrain from smoking for 24 hours prior to the laboratory session on day 23. The primary outcomes are mood and cognitive function during smoking abstinence (vs. smoking as usual). Secondary outcomes include smoking behavior (e.g., cigarettes per day, carbon monoxide) during the 3-week run-up period. These data will lay the foundation for a larger Phase IIb clinical trial.

OBJECTIVES

1. *Overall Objectives*

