The objective of this proof-of-concept pilot study is to establish feasibility and generate measures of effect size to support future research to evaluate metformin as a potential smoking cessation aid and whether HIV status moderates these effects.

2. *Primary Outcome Variable(s)*

The primary outcomes are mood and cognitive function following 24h of smoking abstinence.

3. *Secondary Outcome Variable(s)*

Smoking behavior (e.g., cigarettes per day, carbon monoxide) during the 3-week run-up period.

BACKGROUND

Tobacco smoking is the leading cause of preventable death worldwide and presents a major public health burden [1, 2]. In the United States alone, tobacco smoking accounts for over 400,000 deaths per year, yet 17% of adults continue to smoke [3, 4]. Although the ability of smokers to quit has been aided by new medications and counseling, over 50% of smokers relapse in formal treatment programs within the first week following a quit attempt [5-7] and only 5-10% achieve long-term abstinence [8, 9]. In order to identify novel treatments for smoking cessation, a better understanding of the mechanisms by which relapse occurs is necessary. Two plausible behaviors to target are negative affect and cognitive function. Indeed, in the general population nicotine withdrawal produces increases in negative affect [10-12] and disruption of cognitive function [13-16], often within the first 24 h of abstinence [17, 18]. Importantly, withdrawal-related negative affect [19, 20] and cognitive impairment [21, 22] predict relapse.

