 - b. Anti-psychotic medications as assessed on a case-by-case basis
 - c. Glucophage/metformin
 - d. Glyburide
 - e. Furosemide or digoxin
 - f. Nifedipine

- g. Cationic drugs (e.g., amiloride, digoxin, morphine, procainamide, quinidine, quinine, ranitidine, triamterene, trimethoprim, or vancomycin)
2. Participants who report taking prescription opiate-containing medications (Duragesic/fentanyl patches, Percocet, Oxycontin) will require physician approval prior to confirming final eligibility.
3. Current use of any smoking cessation medications (e.g., Chantix/varenicline, Zyban/bupropion, nicotine replacement therapy/gum/patch).
4. For safety reasons, HIV-infected smokers taking dolutegravir (Tivicay) or drugs that contain dolutegravir (e.g., Triumeq) should not take more than 1000 mg of metformin per day. Therefore, individuals taking dolutegravir will be forced randomized to either the placebo condition or the low dose condition.

Subjects will be instructed to refrain from using any study prohibited drugs/medications (both recreational and prescription) throughout their participation in the study. After final eligibility is confirmed, subjects who report taking contraindicated medication(s) over the course of the study period may only remain eligible if the Study Physician and/or Principal Investigator determines that the contraindicated medication(s) do/did not impact the study design, data quality, and/or subject safety/welfare. Subjects are permitted to take necessary prescription medications not included within the exclusion list during the study.

General Exclusion:

1. Current, anticipated, or pending enrollment in another research program over the next 2-3 months that could potentially affect subject safety and/or the study data/design as determined by the Principal Investigator and/or Study Physician.
2. Not planning to live in the area for the next two months.
3. Color blindness.
4. Any impairment (physical and/or neurological) including visual or other impairment preventing cognitive task performance.
5. Known allergy to study medication.
6. Planned radiologic studies involving the use of intravascular iodinated contrast materials (e.g., intravenous urogram, intravenous cholangiography, angiography, and computed tomography (CT) scans with intravascular contrast materials) during the course of study participation.
7. Inability to provide informed consent or complete any of the study tasks as determined by the Principal Investigator.

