ShIPLEY Institute of Living Scale	X					
Urine Drug Screen	X	X		X	X	
Pregnancy Screen	X	X		X	X	
Depression/Anxiety (HADS)	X	X	X	X	X	
Functional Impairment (PAOFI)	X					
Risk Assessment Battery (HIV+ group only)	X					
BASIS-24	X					
SF-12	X					
Quick Inventory of Depression Symptoms	X					
Liver and Renal Function test	X					
Neuroinflammation (HIV+ group only)		X		X		
Blood Glucose		X		X	X	
Treatment Variables						
Concomitant Medication Review		X	X	X	X	
Medication Side Effects		X	X	X	X	
Pill Count			X	X	X	
Primary Outcomes						
Mood (PANAS)		X	X	X	X (24h)	X (now)
Neurocognitive Test Battery		X		X	X	
Secondary Outcomes						
Cigarette Consumption (TLFB)		X	X	X	X	X
Withdrawal (MNWS-R)		X	X	X	X (24h)	X (now)
Craving (QSU-B)		X	X	X	X (24h)	X (now)
Subjective Effects, Cigarette Ratings (CES, SQ)		X	X	X		X

*Note: Height and weight will be collected at intake visit, weight only will be collected at each subsequent study visit except day 23

^a Only administered if a diagnosis of bipolar disorder is self-reported or revealed via the MINI at intake

^b These visits will be completed remotely via phone or videoconference

enjoyment of airway sensations. The Rose Sensory Questionnaire (SQ), a 9-item Likert-format measure, will be used to assess how much they liked the cigarette smoked and how high in nicotine the cigarettes appeared to be. The questionnaire also includes a diagram of the respiratory tract and asks participants to rate the strength of the cigarette puffs on their tongue, nose, back of mouth and throat, windpipe, and chest. The CES and SQ will be administered at each visit following the Intake.

2. Statistical Analysis

Sample size and analysis. For this analysis we will be estimating summary statistics by group, including means, standard deviations, within-subject correlations, and related confidence intervals. Our sample of 18 per group will yield 95% confidence intervals with limits that fall less than 1/2 SD from the mean. For correlation, the 95% CI length will be no larger than 0.94 if $r=0$, and substantially narrower for $r \neq 0$. Because the goal of this study is to demonstrate feasibility and provide preliminary data, we will not conduct formal hypothesis testing. We will use these measures to estimate interaction effect sizes to plan future research.

3. Confidentiality

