In addition to the side effects mentioned above, other rare side effects of metformin XR have been reported including: lactic acidosis, abdominal pain, constipation, distention abdomen, dyspepsia/heartburn, flatulence, dizziness, headache, upper respiratory infection, and taste disturbance.

All of these side effects shall be queried using a side effects checklist as described above.

Metformin has been shown to be safe and well-tolerated in non-diabetic individuals including normal glucose tolerant, obese African Americans [76]; obese children and adolescents [77]; individuals at risk for developing diabetes [78]; and women with polycystic ovary syndrome [79]. Nevertheless, because metformin has the potential to lower blood glucose levels, even in non-diabetic individuals, participants' blood glucose levels will be monitored at each study visit following the Intake (see Measures: Screening/Covariates for description).

For individuals currently taking anti-retroviral (HAART) medications: There are no known HAART/metformin drug interactions. Specifically, metformin is not metabolized and is excreted unchanged in the urine. The non-nucleoside reverse transcriptase inhibitors, protease inhibitors, raltegravir, and maraviroc are hepatically cleared and are therefore not contraindicated. Because dolutegravir (Tivicay) or drugs that contain dolutegravir (e.g., Triumeq) can double metformin levels, participants taking dolutegravir will be limited to no more than 1000 mg metformin per day. Therefore, individuals taking dolutegravir will be force randomized to either the placebo condition or the low dose condition.

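### If dolutegravir users enrol they cannot receive the high dose, and the analysis has no step for this, so HIV+ high-dose contrasts and any HIV-by-high-dose effect size may be confounded by dolutegravir use

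*Combined protocol and SAP*

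**What the plan says.** Key Exclusion Criteria, Medication, item 4 concerns HIV-infected smokers taking dolutegravir. Although it sits under exclusions, it keeps these people in the trial: "Therefore, individuals taking dolutegravir will be forced randomized to either the placebo condition or the low dose condition". Potential Study Risks repeats the rule and gives the reason: dolutegravir "can double metformin levels, participants taking dolutegravir will be limited to no more than 1000 mg metformin per day". The drug-supply section describes randomization as based on sex and names no other factor.

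The Statistical Analysis section plans "estimating summary statistics by group, including means, standard deviations, within-subject correlations, and related confidence intervals", then adds: "We will use these measures to estimate interaction effect sizes to plan future research". It rules out formal hypothesis testing and names no covariate, stratum or restricted analysis set. Its precision statement is: "Our sample of 18 per group will yield 95% confidence intervals with limits that fall less than 1/2 SD from the mean". Eighteen per group is 54/3, the HIV- sample.

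The Protocol Abstract says of HIV status: "we will explore whether HIV status moderates these effects", and the Overall Objectives repeat that aim. The Background adds an exploratory comparison of 1500 mg with 500 mg.

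**The concern.** Dolutegravir users have zero probability of the high dose. If any enrol, the HIV+ high-dose arm contains none of them, and the HIV+ placebo and low-dose arms contain all of them. That imbalance comes from the allocation rule and does not even out over repeated randomization. Any difference between users and non-users in the outcome analysed then enters the HIV+ high-dose contrasts. Because the rule does not touch HIV- participants, it also passes in full into an HIV-by-high-dose effect size.

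The pilot exists to supply effect sizes for a later trial. A difference between users and non-users could be taken for a dose effect or for HIV moderation, and the confidence interval would not reflect it.

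**Working it through.** **The plan's own figures.** For a mean, the half-width is t(0.975, 17)/sqrt(18) = 2.110/4.243 = 0.497 SD, which agrees with the stated limit of 1/2 SD. For a correlation of zero, 2 x tanh(1.96/sqrt(15)) = 0.934, which agrees with the stated 0.94. At 10 per HIV+ arm (30/3) the half-width for a mean would be 0.715 SD.

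**Inputs.** From the documents: 30 HIV+ and 54 HIV- completers, three arms, users allocated to placebo or low dose only. Assumed, because the documents do not say: a share p = 20/40/60% of HIV+ completers use dolutegravir; non-users are allocated 1:1:1 and users 1:1; no HIV- participant uses it; d is in SD of the outcome analysed.

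**Arm sizes and bias.** HIV+ high dose has 10(1-p) completers. Placebo and low dose each have 10(1-p) + 15p = 10 + 5p. The user share of placebo (and of low dose) is s = 15p/(10 + 5p), against zero in high dose. In size, the bias is s x d.

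| Use p | High v placebo, n | s | Bias at d = 0.25 SD | Bias at d = 0.5 SD |
|---|---|---|---|---|
| 20% | 8 v 11 | 0.27 | 0.07 | 0.14 |
| 40% | 6 v 12 | 0.50 | 0.13 | 0.25 |
| 60% | 4 v 13 | 0.69 | 0.17 | 0.35 |

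High v low has the same s, so the same bias if dolutegravir adds the same amount in every arm. HIV-by-high-dose also takes s x d. If the HIV+ arms were instead held at 10 each, s would be 30/60/90%.

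A simulation of 20,000 runs at 30% use (s = 4.5/11.5 = 0.39) and d = 0.5 SD gave 0.19 SD for HIV+ high v placebo and 0.18 SD for HIV-by-high-dose. Restricting to non-users gave -0.006 SD, and HIV+ low v placebo 0.006 SD.

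**Level or change.** The Primary Outcome section reads as a level on day 23: "The primary outcomes are mood and cognitive function following 24h of smoking abstinence". The Abstract reads as a contrast with usual smoking. For a day 21 to day 23 change, a stable user/non-user difference cancels. At 40% use, a stable 0.5 SD difference gave a simulated bias of about 0.24 on the level and 0.00 on the change. A 0.5 difference in withdrawal response gave about 0.25 on the change, and 0.00 after adjustment.

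**A pooled high v placebo contrast, if one is made.** The user share of placebo is 3/29, 6/30, 9/31, so the unadjusted bias is 0.10/0.20/0.29 x d, plus 0.07/0.15/0.24 x any HIV+/HIV- difference. Adjusting for HIV status alone leaves 0.090/0.143/0.155 x d. Adjusting for HIV status and dolutegravir leaves zero under additivity.

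**Precision of HIV+ high v placebo (SD = 1).**
- Unadjusted variance, 1/n_high + 1/n_placebo: 0.216/0.250/0.327. Half-width 0.98/1.06/1.22 (two-arm df).
- With a dolutegravir indicator fitted to all 30 HIV+, the variance gains s^2/(2 n_placebo s(1-s)): 0.233/0.292/0.413. Half-width 0.99/1.11/1.32 (df 26).
- Restricted to non-users, 2/n_high: 0.250/0.333/0.500. Half-width 1.07/1.29/1.73.

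**When the alternatives win on mean squared error.** The crossover is d = sqrt(variance difference)/s: 0.48/0.41/0.42 SD for adjustment and 0.68/0.58/0.60 SD for restriction.

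**Additivity.** If the low-dose effect in users departs from additivity by e, the adjusted high v placebo estimate is off by 0.14/0.25/0.35 x e.

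**The case against.** The strongest reply is that no harm can be shown. The documents give neither prevalence nor d, and nothing in them suggests that users differ from other HIV+ smokers in mood or cognition after abstinence. Much of the wording, such as the Abstract's "The primary outcomes are mood and cognitive function during smoking abstinence (vs. smoking as usual"), favours a change, for which stable differences cancel. Even at 0.5 SD the bias (0.14 to 0.35) is well below the half-width (0.98 to 1.22), and there is no test or decision rule. All of this stands, and it limits the weight of the point. It does not remove the structural gap: the comparison is not fully randomized, and no section of the documents handles that.

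It is also fair that the reach is narrower than it may seem. The design names medication as its one between-subjects factor, so the planned interaction effect sizes may mean medication by abstinence. HIV moderation is only to be explored, and no pooled HIV+/HIV- contrast is described. The pooled figures above therefore apply only if someone makes that contrast.

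The remedy has limits too. At d = 0.25 SD both alternatives have higher mean squared error than the unadjusted estimate. At 0.5 SD restriction still does (0.250 v 0.235, 0.333 v 0.312, 0.500 v 0.447). If HIV+ arms were held at 10 each with 60% use, restriction would leave 10 v 1, with half-widths of 0.94 unadjusted, 1.66 adjusted and 2.37 restricted. Restriction is therefore only an optional check.

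A reader might infer that users per arm will be withheld. The Statistical Analysis section is merely silent on descriptive tables, and medication use is recorded.

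**Conclusion.** The point holds, conditionally. If dolutegravir users enrol, HIV+ high v placebo, HIV+ high v low and any HIV-by-high-dose effect size carry a bias of 0.27/0.50/0.69 x d at 20/40/60% use. This rests on 30 HIV+ completers and the assumed allocation ratios. The bias is zero if d is zero; for a day 21 to day 23 change, d means a difference in withdrawal response only.

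Two stronger readings are tempting and unsupported. One is that the HIV+ high-dose results will be biased by a material amount: prevalence and d are both absent from the documents, so the size is unknown. The other is that every comparison is affected. HIV- contrasts are not. HIV+ low dose v placebo is not either, provided users and non-users share one placebo:low ratio; the documents do not state that ratio, but nothing in them suggests it differs.

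The plan should be changed because following it as written yields contrasts that are not fully randomized, and a better-founded estimate costs little.

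**What to change.** Leave the safety restriction as it is. In the Statistical Analysis section, state that:

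1. wherever HIV+ high-dose or HIV-by-high-dose effect sizes are presented, an estimate adjusted for a dolutegravir indicator is reported beside the unadjusted one;
2. if a pooled high-dose contrast is made, the adjusted version includes HIV status as well as the indicator;
3. restriction to participants eligible for all three arms is an optional sensitivity check;
4. the number of dolutegravir users in each arm is reported.

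No new data are needed: medication is reviewed at Intake and tracked at each time-point. The analysis text sits inside the IRB protocol, so an amendment may be required.

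The price is precision. At 20/40/60% use, adjustment adds 0.01 to 0.10 SD to the HIV+ high v placebo half-width, and takes HIV-by-high-dose from 1.14/1.20/1.32 to 1.17/1.26/1.44 SD. Restriction can widen the HIV+ high v placebo interval by about 42% (1.22 to 1.73 SD at 60% use). Adjustment also assumes that dolutegravir shifts the outcome equally in every arm. That is uncertain, since the protocol itself says dolutegravir can double metformin levels, and it is a reason to show both estimates.

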We hypothesize that because HIV-infected individuals are more likely to experience mood disturbance [36, 37] and cognitive dysfunction [38, 39], MET (vs. placebo) will attenuate increases in mood disturbance and cognitive dysfunction (verbal and working memory, executive function, and response inhibition) following 24 hours of smoking abstinence among HIV-infected smokers. We will also test whether MET (vs. placebo) reduces smoking behavior (e.g., cigarettes per day, carbon monoxide) during the 3-week drug run-up. Lastly, we will explore whether there is an added benefit to increasing the dose to 1500 mg (vs. 500 mg) without corresponding adverse effects. The proposed study is uniquely positioned to identify a potential new smoking cessation treatment for a population of smokers with high smoking relapse rates.

CHARACTERISTICS OF THE STUDY POPULATION

1. Target Population

Adult, non-treatment seeking smokers (HIV-: n=54; and HIV+: n=30), between the ages of 18-65, reporting consumption of at least 10 cigarettes per day for at least the past 6 months will be the target population for the study. HIV-infected smokers have been diagnosed with HIV/AIDS (identified through the UPENN CFAR Clinical Core, UPHS PennChart reviews and community-based HIV/AIDS organizations and events; see specific criteria below) and HIV-uninfected smokers will have no diagnosis of HIV, either via blood test (see recruitment strategy below) or self-report.

2. Accrual

One hundred and sixty HIV- and ninety HIV+ subjects will be enrolled in order to have 54 HIV- and 30 HIV+ smokers complete all sessions, accounting conservatively for 30% attrition. Participants will first be screened over the phone and then complete an in-person Intake to ensure final eligibility. Enrolled participants will be randomized to one of the three groups: low dose (500 mg), high dose (1500 mg), or placebo.

3. Key Inclusion Criteria

Eligible subjects will be males and females:

1. 18 years of age or older who self-report smoking at least 5 cigarettes (menthol and non-menthol) per day, on average for the past 6 months.
2. **HIV status**
 - a) HIV-infected smokers: diagnosed with HIV infection and exhibiting viral load of less than or equal to 1000 copies/mL and CD4+ counts of greater than or equal to 200 cells/mm³ within 6 months prior to enrollment.
 - b) HIV-uninfected smokers: no diagnosis of HIV, either via blood test or self-report.
3. Must not currently be interested in quitting smoking.

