Once the Study Physician ([name]) or Nurse Practitioner signs the prescription, medication kits will be ordered and picked up from IDS by a member of the research staff. These kits will be stored in a locked cabinet at our center. Medication will be stored at CIRNA as per manufacturer's guidelines. If needed, staff may request that IDS ship the study medication directly to a subject. IDS will oversee the randomization of subjects to a medication group based on sex, and will label each kit with the subject's study ID number and PRN. The PRN and study ID number must match for each blister pack a subject receives. Each medication kit will consist of 23 days of metformin or placebo (see above for dosing guidelines). To maintain double-blind procedures, all groups will take the same number of pills each day. For example, when the high dose group reaches the 1500 mg dose they will take 3 active pills containing 500 mg each of metformin, the low dose group will take 1 active pill containing 500 mg metformin and 2 placebo pills each day, and the placebo group will take 3 placebo pills.

Regular study drug reconciliation will be performed to document drug assigned, drug consumed, and drug remaining. This reconciliation will be logged on the drug reconciliation form and signed by the research staff member who completed the reconciliation.

At the completion of the study, there will be a final reconciliation of drug shipped, drug consumed, and drug remaining. This reconciliation will be logged on the drug reconciliation form, signed and dated by the research staff. Any discrepancies noted will be investigated, resolved, and documented prior to return or destruction of unused study drug. Drug destroyed on site will be documented in the study files.

SUICIDAL IDEATION

The C-SSRS will be administered remotely (via phone or videoconferencing) as part of the Intake visit by a trained member of the staff. Individuals who endorse current (past month) suicidal ideation or lifetime suicidal behavior will be ineligible to participate. Because these assessments may cause an adverse emotional reaction, staff will be trained to deal with such reactions and to provide additional referrals if needed. If necessary, referrals to appropriate psychological services will be provided. In addition, the CES-D will be administered at follow-up visits to monitor changes in depressive symptoms throughout the trial.

STUDY PROCEDURES

1. Procedures

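### HIV status is not a randomisation stratum although its moderating role is a stated aim, so the HIV+ split over arms is uncontrolled and is also shifted away from high dose by the dolutegravir rule

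*Combined protocol and SAP*

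**What the plan says.** Under Drugs or Devices, in the paragraphs on supply, packaging and dispensing, the protocol states that "IDS will oversee the randomization of subjects to a medication group based on sex". That is the only mention of a randomisation factor. No block size, allocation ratio, or separate list for HIV+ and HIV- participants is described.

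HIV status matters to the aims. The Overall Objectives are to "evaluate metformin as a potential smoking cessation aid and whether HIV status moderates these effects", and the Protocol Abstract says "we will explore whether HIV status moderates these effects". The Statistical Analysis section plans summary statistics by group without hypothesis tests, and lists interaction effect sizes among its outputs. It names no covariates.

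The Accrual section sets totals by HIV status. For the intake numbers it states: "One hundred and sixty HIV- and ninety HIV+ subjects will be enrolled". The reason it gives for those numbers is a completion target, namely "in order to have 54 HIV- and 30 HIV+ smokers complete all sessions, accounting conservatively for 30% attrition". On allocation it says only: "Enrolled participants will be randomized to one of the three groups: low dose (500 mg), high dose (1500 mg), or placebo". These quotas fix how many HIV+ smokers take part, not how they divide over arms.

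One rule does act on that division. Under Key Exclusion Criteria, Medication item 4, and again under Potential Study Risks, "individuals taking dolutegravir will be forced randomized to either the placebo condition or the low dose condition". The share of HIV+ smokers on dolutegravir is not given, and nothing says how the rule is built into the allocation list or handled in the analysis.

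**The concern.** The Background and the Abstract expect HIV infection to worsen mood, cognition and the effects of abstinence on both, which are the primary outcomes. A factor that is both prognostic and a moderator of interest would usually be a stratum, particularly when its smaller level has about 30 completers over three arms.

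Two things are at stake. The first is the size of the smallest HIV+ cell, in a pilot whose product is precision of estimates. The second is comparability: the dolutegravir rule moves HIV+ smokers from high dose to the other two arms, so those arms differ from high dose in HIV share and, among HIV+ smokers, in antiretroviral regimen. The second effect is not random and does not average out.

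**Working it through.** **Inputs from the protocol.** Completers: 54 HIV- and 30 HIV+. Enrolled: 160 and 90. Three arms. Attrition 30%. 18 per group in Statistical Analysis.

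**Assumptions.** 1:1:1 allocation; loss unrelated to arm; dolutegravir share f of 20-40% among HIV+ (the protocol gives none).

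**1. The plan's own precision figure.** The half-width of a 95% CI for a mean, in SD units, is t(0.975, n-1)/√n. At n = 18: 2.110/√18 = 0.497, so the stated limit of under half an SD reproduces. But 18 = 54/3, the HIV- cell. For HIV+ cells:

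| n | Half-width (SD) |
|---|---|
| 10 | 2.262/√10 = 0.72 |
| 7 | 2.447/√7 = 0.92 |
| 6 | 2.571/√6 = 1.05 |

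**2. How many are randomised.** At 30% loss, 30/0.70 = 42.9, so 43 HIV+, and 54/0.70 = 77.1, so 78 HIV-. The enrolment targets imply more: 1 - 30/90 = 67% and 1 - 54/160 = 66% loss. Both cases are shown because the protocol does not say how many of those enrolled reach randomisation.

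**3. Chance split of 30 HIV+ completers, like for like.** Arm totals are balanced in every row. Without an HIV stratum, the HIV+ completers are a random draw from the balanced arms (hypergeometric, simulated). With it, the HIV+ participants are themselves balanced over arms, then 30 complete at random.

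| Case | Stratum | Randomised per arm | P(smallest HIV+ arm ≤ 7) |
|---|---|---|---|
| 30% loss | none | 40/40/41 (all) | 0.39 |
| 30% loss | HIV | 14/14/15 (HIV+) | 0.13 |
| All enrolled randomised | none | 83/83/84 (all) | 0.44 |
| All enrolled randomised | HIV | 30/30/30 (HIV+) | 0.35 |

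**4. What an uneven split costs.** The SE of a two-arm difference among HIV+ smokers is √(1/a + 1/b) SD.
- 10/10: √0.2 = 0.447.
- 7/13: 0.469, ratio 1.05.
- 6/12: 0.500, ratio 1.12.

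For an interaction against 18 HIV- per arm, √(1/a + 1/b + 2/18) is 0.558 at 10/10 and 0.575 at 7/13, ratio 1.03.

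**5. The dolutegravir shift.** Expected high-dose HIV+ cell = 30(1 - f)/3. Each other arm gets that plus 30f/2. HIV share uses 18 HIV- per arm.

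| f | High dose HIV+ | Each other arm HIV+ | HIV share, high dose | HIV share, others |
|---|---|---|---|---|
| 0.2 | 8 | 8 + 3 = 11 | 8/26 = 31% | 11/29 = 38% |
| 0.4 | 6 | 6 + 6 = 12 | 6/24 = 25% | 12/30 = 40% |

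Among HIV+ smokers in placebo or low dose, 3/11 = 27% to 6/12 = 50% would be on dolutegravir, against none in high dose. An HIV stratum changes none of these expected values.

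**6. Size of the resulting shift.** If HIV status moved an outcome by 0.5 SD (assumption), gaps of 7 and 15 points would shift an unadjusted pooled contrast with high dose by 0.07 × 0.5 = 0.035 SD and 0.15 × 0.5 = 0.075 SD. With 28 per arm, the SE of that contrast is √(2/28) = 0.27 SD.

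**The case against.** The strongest reply is that this is a feasibility pilot without hypothesis tests, that HIV moderation is exploratory, and that medication is the only between-subjects factor in the Design section. Even a perfect 10/10/10 gives a half-width of 0.72 SD, so small cells limit the HIV+ estimates more than uneven ones do. That stands, and it limits the weight of the point.

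Second, the Statistical Analysis section describes no pooled arm contrast, and a stable HIV difference would largely cancel in a comparison of abstinence with smoking as usual. The first part stands: adjustment applies only to whatever pooled contrasts are made. The second stands only in part, because the Abstract suggests that HIV infection may exacerbate abstinence effects, and that would not cancel.

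Third, timing. Version 15 is dated August 2020 and the last completers are projected for January 2021, so a new list reaches few participants. That stands.

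Several stronger readings are tempting and not supported:
- A reader might take 10 HIV+ smokers per arm as a planned number. It is 30/3 under an unstated ratio.
- A reader might set simple randomisation of 30 (smallest arm 7 or fewer with probability 0.48) against blocked allocation (0.13). That mixes two changes. The like-for-like contrasts are in step 3, and one of them is only 0.44 to 0.35.
- A reader might say that chance imbalance biases the dose contrasts. Under randomisation it adds variance; only the dolutegravir rule acts systematically.
- A reader might expect an HIV stratum to restore the high-dose HIV+ cell. It does not, nor does it guarantee 10 completers per arm.

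**Conclusion.** The point holds as a modest, cheaply corrected design gap. Sex is the only randomisation factor named, so the arm split of the HIV+ group is uncontrolled. Reading the wording as stratification by sex is reasonable, though the text is loose.

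An HIV stratum would cut the chance of a smallest HIV+ cell of 7 or fewer by about 26 points at 30% loss (0.39 - 0.13), but by only about 9 if 90 are randomised and 30 complete (0.44 - 0.35). The gain in standard error is small.

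The more durable problem is the dolutegravir rule, which makes the high-dose arm differ systematically in HIV share and in regimen. Its size depends wholly on f. At 20-40% the HIV share differs by about 7 to 15 points, and the shift in a pooled contrast is small against its SE unless the HIV effect is well above the assumed 0.5 SD. Because the protocol may largely be run by now, the analysis provisions matter more than the list.

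**What to change.** **Allocation, for remaining participants.** Have the pharmacy service stratify by HIV status as well as sex, and state the ratio and blocking. Keep dolutegravir users in a separate two-arm list that leaves the existing restriction unchanged.

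**Analysis.** Add to the Statistical Analysis section that:
- any pooled arm contrast is adjusted for HIV status and sex;
- HIV-by-arm counts are reported, both randomised and completing;
- contrasts with high dose use only participants who were eligible for all three arms, or are shown with and without dolutegravir users. Low dose against placebo can keep them, provided the two-arm list is 1:1.

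**Cost.** No extra participants or visits; HIV status is known before randomisation. There will be a few more part-filled blocks. Restricting high-dose contrasts shrinks the comparison group: at f of 20-40%, the expected HIV+ comparison becomes 8 against 8 to 6 against 6, with SE √(2/8) = 0.50 to √(2/6) = 0.58 SD, against 0.46 (8 and 11) to 0.50 (6 and 12) when dolutegravir users are kept. That loss buys a comparison between participants who could have received either treatment.
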